Please respond to each item by selecting one response below. Strongly Strongly disagree Disagree Neutral Agree agree I tend to bounce back quickly after hard times. 0 0 0 \bigcirc \bigcirc \bigcirc \bigcirc \bigcirc \bigcirc I have a hard time making it through stressful events. It does not take me long to recover from a stressful event. \bigcirc \bigcirc \bigcirc \bigcirc \bigcirc It is hard for me to snap back when something bad happens. 0 \bigcirc \bigcirc \bigcirc \bigcirc I usually come through difficult times with little trouble. \bigcirc \bigcirc \bigcirc 0 \bigcirc \bigcirc I tend to take a long time to get over set-backs in my life. \bigcirc \bigcirc \bigcirc \bigcirc

ECR-RS (Experiences in Close Relationships - Relationship Structures)

Please read each of the following statements and rate the extent to which you believe each statement best describes your feelings about **close relationships in general**.

	Strongly disagree	2	3	4	5	6	Strongly agree
It helps to turn to people in times of need.	0	0	0	0	0	0	0
I usually discuss my problems and concerns with others.	\circ	\bigcirc	\bigcirc	0	0	\bigcirc	0
I talk things over with people.	0	\bigcirc	\bigcirc	\bigcirc	\bigcirc	\bigcirc	0
I find it easy to depend on others.	0	\bigcirc	\bigcirc	\bigcirc	\bigcirc	\bigcirc	0
I don't feel comfortable opening up to others.	0	\bigcirc	\bigcirc	\bigcirc	\bigcirc	\bigcirc	0
I prefer not to show others how I feel deep down.	0	\bigcirc	\bigcirc	\bigcirc	\bigcirc	\bigcirc	0
I often worry that other people do not really care for me.	0	\bigcirc	\bigcirc	\bigcirc	\bigcirc	\bigcirc	\bigcirc
I'm afraid that other people may abandon me.	0	\bigcirc	\bigcirc	\bigcirc	\bigcirc	\bigcirc	0
I worry that others won't care about me as much as I care about them.	0	\bigcirc	\bigcirc	\bigcirc	\bigcirc	\bigcirc	\bigcirc

MAIA (Interoceptive Awareness)

Below you will find a list of statements.

Please indicate how often each statement applies to you generally in daily life:

	Never	1	2	3	4	Always
When I am tense I notice where the tension is located in my body.	0	0	0	0	0	0
I notice when I am uncomfortable in my body.	0	0	\bigcirc	0	\bigcirc	0
I notice where in my body I am comfortable.	0	0	0	0	\bigcirc	0
I notice changes in my breathing, such as whether it slows down or speeds up.	0	\bigcirc	0	0	0	\bigcirc
I ignore physical tension or discomfort until they become more severe.	0	\bigcirc	0	0	0	\bigcirc
I distract myself from sensations of discomfort.	0	0	\bigcirc	0	\bigcirc	0
When I feel pain or discomfort, I try to power through it.	0	\bigcirc	\bigcirc	0	\bigcirc	\bigcirc
I try to ignore pain.	0	0	0	0	0	0
I push feelings of discomfort away by focusing on something.	0	\bigcirc	\bigcirc	0	\bigcirc	\bigcirc
When I feel unpleasant body sensations, I occupy myself with something else so I don't have to feel them.	0	\bigcirc	\circ	\bigcirc	\bigcirc	\circ
When I feel physical pain, I become upset.	0	\bigcirc	\bigcirc	0	\bigcirc	0
I start to worry that something is wrong if I feel any discomfort.	0	\bigcirc	0	0	0	\bigcirc

Below you will find a list of statements.

Please indicate how often each statement applies to you generally in daily life:

	Never	1	2	3	4	Always
I can notice an unpleasant body sensation without worrying about it.	0	\bigcirc	0	0	0	\bigcirc
I can stay calm and not worry when I have feelings of discomfort or pain.	0	\bigcirc	\bigcirc	0	\bigcirc	\bigcirc
When I am in discomfort or pain I can't get it out of my mind.	0	\bigcirc	0	0	\bigcirc	\bigcirc
I can pay attention to my breath without being distracted by things happening around me.	0	\bigcirc	\bigcirc	0	\bigcirc	\bigcirc
I can maintain awareness of my inner bodily sensations even when there is a lot going on around me.	0	\bigcirc	\bigcirc	0	\bigcirc	\circ
When I am in conversation with someone, I can pay attention to my posture.	0	\bigcirc	0	\bigcirc	\bigcirc	\bigcirc
I can return awareness to my body if I am distracted.	0	0	0	0	0	0
I can refocus my attention from thinking to sensing my body.	0	\circ	0	\bigcirc	\bigcirc	\bigcirc
I can maintain awareness of my whole body even when a part of me is in pain or discomfort.	0	\bigcirc	0	\bigcirc	\bigcirc	\bigcirc
I am able to consciously focus on my body as a	0	0	0	0	0	0

whole.							
I notice how my body changes when I am angry.	0	0	0	\bigcirc	\bigcirc	\bigcirc	
When something is wrong in my life I can feel it in my body.	0	\bigcirc	0	\bigcirc	0	0	
I notice that my body feels different after a peaceful experience.	0	\bigcirc	\bigcirc	\bigcirc	\bigcirc	0	

Below you will find a list of statements.

Please indicate how often each statement applies to you generally in daily life:

	Never	1	2	3	4	Always
I notice that my breathing becomes free and easy when I feel comfortable.	0	0	0	0	0	0
I notice how my body changes when I feel happy / joyful.	0	\bigcirc	0	\bigcirc	\bigcirc	\bigcirc
When I feel overwhelmed I can find a calm place inside.	0	0	0	0	0	\bigcirc
When I bring awareness to my body I feel a sense of calm.	0	0	\bigcirc	0	0	\bigcirc
I can use my breath to reduce tension.	0	0	0	0	0	0
When I am caught up in thoughts, I can calm my mind by focusing on my body/breathing.	0	\bigcirc	0	0	0	\bigcirc
I listen for information from my body about my emotional state.	0	\bigcirc	0	\bigcirc	\bigcirc	\bigcirc
When I am upset, I take time to explore how my body feels.	0	\bigcirc	0	\bigcirc	\bigcirc	\bigcirc
I listen to my body to inform me about what to do.	0	0	0	0	0	0
I am at home in my body.	0	\bigcirc	0	0	\bigcirc	0
I feel my body is a safe place.	0	0	0	0	0	0
I trust my body sensations.	0	0	0	0	0	0
	I					

FFMQ (Five Facets of Mindfulness)

Choose the best response that describes your opinion of what i	s gene	erally t	true for y	ou.	
	Never or very rarely true	Rarely true	Sometimes true	Often true	Very often or always true
When I'm walking, I deliberately notice the sensations of my body moving.	0	0	0	0	0
I'm good at finding words to describe my feelings.	0	\bigcirc	0	\bigcirc	\bigcirc
I criticize myself for having irrational or inappropriate emotions.	0	\bigcirc	0	\bigcirc	\bigcirc
I perceive my feelings and emotions without having to react to them.	0	\bigcirc	0	\bigcirc	\bigcirc

When I do things, my mind wanders off and I'm easily distracted.	0	\bigcirc	\bigcirc	\bigcirc	\bigcirc
When I take a shower or bath, I stay alert to the sensations of water on my body.	0	\bigcirc	\bigcirc	\bigcirc	\bigcirc
I can easily put my beliefs, opinions, and expectations into words.	0	\bigcirc	\bigcirc	\bigcirc	\bigcirc
I don't pay attention to what I'm doing because I'm daydreaming, worrying, or otherwise distracted.	\bigcirc	0	\bigcirc	\bigcirc	0
I watch my feelings without getting lost in them.	0	\bigcirc	\bigcirc	\bigcirc	\bigcirc
I tell myself I shouldn't be feeling the way I'm feeling.	0	\bigcirc	\bigcirc	\bigcirc	\bigcirc
I notice how foods and drinks affect my thoughts, bodily sensations, and emotions.	0	\bigcirc	\bigcirc	\bigcirc	\bigcirc
It's hard for me to find the words to describe what I'm thinking.	0	\bigcirc	\bigcirc	\bigcirc	\bigcirc
I am easily distracted.	0	\bigcirc	\bigcirc	\bigcirc	\bigcirc
Please select 'Very often' for this response.	0	\bigcirc	\bigcirc	\bigcirc	\bigcirc

Choose the best response that describes your opinion of what is generally true for you.

	Never or very rarely true	Rarely true	Sometimes true	Often true	Very often or always true
I believe some of my thoughts are abnormal or bad and I shouldn't think that way.	0	0	0	0	0
I pay attention to sensations, such as the wind in my hair or sun on my face.	0	\bigcirc	\bigcirc	\bigcirc	\bigcirc
I have trouble thinking of the right words to express how I feel about things.	0	\bigcirc	\bigcirc	\bigcirc	0
I make judgments about whether my thoughts are good or bad.	0	\bigcirc	\bigcirc	\bigcirc	0
I find it difficult to stay focused on what's happening in the present.	0	\bigcirc	0	\bigcirc	0
When I have distressing thoughts or images, I "step back" and am aware of the thought or image without getting taken over by it.	0	0	\bigcirc	\bigcirc	\bigcirc
I pay attention to sounds, such as clocks ticking, birds chirping, or cars passing.	0	\bigcirc	\bigcirc	\bigcirc	\bigcirc
In difficult situations, I can pause without immediately reacting.	0	\bigcirc	\bigcirc	\bigcirc	0
When I have a sensation in my body, it's difficult for me to describe it because I can't find the right words.	0	0	\bigcirc	\bigcirc	\bigcirc
It seems I am "running on automatic" without much awareness of what I'm doing.	0	\bigcirc	\bigcirc	\bigcirc	\bigcirc
When I have distressing thoughts or images, I feel calm soon after.	0	\bigcirc	\bigcirc	\bigcirc	\bigcirc
I tell myself that I shouldn't be thinking the way I'm thinking.	0	\bigcirc	0	\bigcirc	0
I notice the smells and aromas of things.	0	0	0	0	0

Choose the best response that describes your opinion of what is generally true for you.

	Never or very rarely true	Rarely true	Sometimes true	Often true	Very often or always true
Even when I'm feeling terribly upset, I can find a way to put it into words.	0	\bigcirc	0	0	0

I rush through activities without being really attentive to them.	\bigcirc	0	\bigcirc	\bigcirc	\bigcirc
When I have distressing thoughts or images I am able just to notice them without reacting.	\bigcirc	\bigcirc	\bigcirc	\bigcirc	0
I think some of my emotions are bad or inappropriate and I shouldn't feel them.	\bigcirc	\bigcirc	0	\bigcirc	0
I notice visual elements in art or nature, such as colors, shapes, textures, or patterns of light and shadow.	\bigcirc	0	\bigcirc	0	\bigcirc
My natural tendency is to put my experiences into words.	\bigcirc	\bigcirc	\bigcirc	\bigcirc	0
When I have distressing thoughts or images, I just notice them and let them go.	\bigcirc	\bigcirc	\bigcirc	\bigcirc	0
I do jobs or tasks automatically without being aware of what I'm doing.	\bigcirc	\bigcirc	\bigcirc	\bigcirc	0
When I have distressing thoughts or images, I judge myself as good or bad, depending what the thought/image is about.	\bigcirc	\bigcirc	\bigcirc	0	\bigcirc
I pay attention to how my emotions affect my thoughts and behavior.	\bigcirc	\bigcirc	\bigcirc	\bigcirc	\bigcirc
I can usually describe how I feel at the moment in considerable detail.	\bigcirc	\bigcirc	\bigcirc	\bigcirc	0
I find myself doing things without paying attention.	\bigcirc	\bigcirc	\bigcirc	\bigcirc	\bigcirc
I disapprove of myself when I have irrational ideas.	\bigcirc	\bigcirc	\bigcirc	\bigcirc	\bigcirc

TE (Trauma Exposure and Training Questions)

Overall, how much of your work involves (directly or indirectly) engaging with traumatized individuals or traumatic material?
◯ A great deal
O A lot
O A moderate amount
◯ A little
O None at all

How much training have you received on primary or secondary trauma (including topics like vicarious trauma, secondary traumatic stress, burnout, and moral distress)?
A great deal
A lot
A moderate amount
A little
None at all

Altogether, how effective were your trainings on primary or secondary trauma (including topics

like vicarious trauma, secondary traumatic stress, burnout, and moral distress)?
C Extremely effective
◯ Very effective
O Moderately effective
Slightly effective
◯ Not effective at all
Do you want more training on secondary trauma (including topics like vicarious trauma, secondary traumatic stress, burnout, and moral distress)?
secondary traumatic stress, burnout, and moral distress)?
secondary traumatic stress, burnout, and moral distress)?
secondary traumatic stress, burnout, and moral distress)? Definitely yes Probably yes
secondary traumatic stress, burnout, and moral distress)? Definitely yes Probably yes Might or might not

FE (Feedback)

Are there any factors affecting your answers that we should know about (e.g., a health issue or language barrier)?

Please provide any other feedback you would like to share.

Identifiers

Thank you for participating in our survey. We would like to email you an Amazon.com eGift Card. To do so, we need you to complete the following questions.

Please allow one week for us to email you the eGift Card. Thanks for your patience with us!

What is your first name?

What is your last name?

What is your phone number (e.g., XXX-XXX-XXXX)?

What is your email address? (This is where we will send your e-gift card.)

Please verify your email address.

Official Title: Somatic Mindfulness Training for a Healthy Workforce: Student Pilot Sample

NCT Number: NCT04122534

Document Date: 08/08/2019

STATISTICAL ANALYSIS PLAN

For each outcome measure (i.e., STSS, PCL-5), most analyses will simply involve calculating descriptive statistics for each wave of data collection. We are pilot testing materials using a small sample and findings will help inform future statistical designs and power needs.

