Work Demographics*	WD	7
Maslach Burnout Inventory – General Version*	MBI-G	16
Maslach Burnout Inventory – General Student Version*	MBI-GS	17
Maslach Burnout Inventory – Student Version*	MBI-S	16
Secondary Traumatic Stress Scale	STSS	18
The PTSD Checklist for DSM-5	PCL-5	20
Body Mass Index	BMI	2
Health Related Quality of Life	HRQoL	4
Autoimmune Diagnosis	AD	1
Patient Health Questionnaire – Somatic Symptom Severity	PHQ-15	15
AUDIT Alcohol Questionnaire	AUDIT	10
Tobacco, Alcohol, Prescription and Other Substance Use Tool	TAPS	4
Jenkins Sleep Scale	JSS	4
Generalized Anxiety Disorder	GAD-7	7
Patient Health Questionnaire – Depression	PHQ-8	8
Mental Health Specialist	MHS	1
Interpersonal Reactivity Index	IRI	28
BRFSS Adverse Childhood Experience (ACE) Module	BRFSS ACE	11
Brief Resilience Scale	BRS	6
Experiences in Close Relationships - Relationship Structures	ECR-RS	9
Multidimensional Assessment of Interoceptive Awareness	MAIA	37
Five Facets of Mindfulness Questionnaire	FFMQ	20
Trauma Exposure and Training	TE	4
Feedback	FE	2

Note: *All items may not actually appear in each survey.

C. DECEPTION - If any deception (withholding of complete information) is required for the validity of this activity, explain why this is necessary and attach debriefing statement.

No deceptive practices will be used.

- D. SUBJECTS
 - Approximate number and ages How Many Subjects: 65 Age Range of Subjects: 18 years and older How Many Normal/Control: n/a Age Range of Normal/Control: 18 years and older
 - 2. Criteria for selection:

Study participants must be either students at MSU or working or volunteering in a victim service profession or organization. All participants must be 18 years or older.

3. Criteria for exclusion:

For the first two cohorts, those who are not undergraduate students at Montana State University will be excluded from data collection. For the third cohort, study participants not working or volunteering in a victim service profession or organization will be excluded from data collection. Anyone who is not 18 years or older will be excluded from all parts of the study.

4. Source of Subjects (including patients):

For cohorts one and two, study participants will be recruited in the classroom. Both Drs. [name] and [name] are popular teachers who attract students interested in issues of trauma and mindfulness. For cohort 3, community contacts, victim service organizations, and community advisory board members will help with recruitment.

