Do you consider yourself to be a veteran? Yes

🔿 No

Do you consider yourself to be an NCAA athlete?	
◯ Yes	
○ No	

Do you consider yourself to be a student with a documented disability? Check all that apply.

No	
O ADHD/ADD	
Learning disability	
Physical disability	
Psychological disability	
Traumatic brain injury	
Other:	

MBI-S (Maslach Burnout Inventory - Student Version)

Below are 17 statements of university-related feelings. Please read each statement and decide if you ever feel this way about your academic work. If you have had this feeling, indicate how often you feel it by indicating the choice that best describes how frequently you feel that way.

	Never	A few times a year or less	Once a month or less	A few times a month	Once a week	A few times a week	Every day
I feel emotionally drained by my studies.	0	\bigcirc	0	0	0	0	\bigcirc
I feel used up at the end of the day at the university.	\bigcirc	\bigcirc	\bigcirc	\bigcirc	\bigcirc	\bigcirc	\bigcirc
I feel tired when I get up in the morning and have to face another day at the university.	\bigcirc	0	\bigcirc	\bigcirc	\bigcirc	\bigcirc	\bigcirc
Attending classes all day is really a strain for me.	\bigcirc	\bigcirc	\bigcirc	\bigcirc	\bigcirc	\bigcirc	\bigcirc
I can effectively solve the problems that arise in my studies.	\bigcirc	0	\bigcirc	\bigcirc	\bigcirc	\bigcirc	\bigcirc
I feel burned out from my studies.	\bigcirc	\bigcirc	\bigcirc	\bigcirc	\bigcirc	\bigcirc	\bigcirc
I feel I am making an effective contribution in class.	0	\bigcirc	\bigcirc	\bigcirc	\bigcirc	\bigcirc	0
I have become less interested in my studies since my enrollment.	0	0	0	\bigcirc	0	0	0

Copyright ©1996 Wilmar B. Schaufeli, Michael P. Leiter, Christina Maslach & Susan E. Jackson. All rights reserved in all media. Published by Mind Garden, Inc., www.mindgarden.com

On this page are statements of job-related feelings. Please read each statement carefully and decide if you ever feel this way about your job.

A few times a Once a

A few times a

A few times a

	Never	year or less	month or less	month	Once a week	week	Everyday
I have become less enthusiastic about my studies.	0	\bigcirc	0	0	\bigcirc	\bigcirc	0
In my opinion, I am a good student.	0	\bigcirc	\bigcirc	\bigcirc	\bigcirc	\bigcirc	\bigcirc
I feel exhilarated when I accomplish something at the university.	0	\bigcirc	0	\bigcirc	\bigcirc	0	0
I have accomplished many worthwhile things in my studies.	0	\bigcirc	\bigcirc	\bigcirc	\bigcirc	\bigcirc	\bigcirc

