I just want to get my work done and not be bothered.	0	\bigcirc	\bigcirc	\bigcirc	\bigcirc	\bigcirc	\bigcirc
I have become more cynical about whether my university work contributes to anything.	\bigcirc	\bigcirc	0	\bigcirc	\bigcirc	0	\circ
I doubt the significance of my studies	0	\bigcirc	\bigcirc	\bigcirc	\bigcirc	\bigcirc	\bigcirc
While working at the university, I feel confident that I am effective at getting things done.	0	\bigcirc	0	0	0	0	0

Copyright ©1996 Wilmar B. Schaufeli, Michael P. Leiter, Christina Maslach & Susan E. Jackson. All rights reserved in all media. Published by Mind Garden, Inc., www.mindgarden.com

MBI-GS (Maslach Burnout Inventory - General Student Version)

Do you currently work (for a wage or as a volunteer)?

Yes, I currently work either for a wage or as a volunteer.

No, I do not currently work or volunteer.

On this page are statements of job-related feelings. Please read each statement carefully and decide if you ever feel this way about your job.

	Never	A few times a year or less	Once a month or less	A few times a month	Once a week	A few times a week	Every day
I feel emotionally drained from my work.	0	0	0	0	\bigcirc	0	0
I feel used up at the end of the workday.	0	\bigcirc	\bigcirc	\bigcirc	\bigcirc	\bigcirc	\bigcirc
I feel tired when I get up in the morning and have to face another day on the job.	0	\bigcirc	\bigcirc	\bigcirc	\bigcirc	\bigcirc	0

Working all day is really a strain for me.	0	0	0	0	0	0	0	
I can effectively solve the problems that arise in my work.	0	0	\bigcirc	\bigcirc	0	\bigcirc	0	
I feel burned out from my work.	0	\bigcirc	\bigcirc	\bigcirc	\bigcirc	\bigcirc	\bigcirc	
I feel I am making an effective contribution to what this organization does.	0	\bigcirc	\bigcirc	\bigcirc	\bigcirc	\bigcirc	\bigcirc	
I have become less interested in my work since I started this job.	0	\bigcirc	\bigcirc	\bigcirc	\bigcirc	\bigcirc	\bigcirc	

Copyright ©1996 Wilmar B. Schaufeli, Michael P. Leiter, Christina Maslach & Susan E. Jackson. All rights reserved in all media. Published by Mind Garden, Inc., www.mindgarden.com

On this page are statements of job-related feelings. Please read each statement carefully and decide if you ever feel this way about your job.

	Never	A few times a year or less	Once a month or less	A few times a month	Once a week	A few times a week	Every day
I have become less enthusiastic about my work.	0	0	0	0	0	0	0
In my opinion, I am good at my job.	0	\bigcirc	\bigcirc	\bigcirc	\bigcirc	\bigcirc	0

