I feel exhilarated when I accomplish something at work.	0	\bigcirc	\bigcirc	\bigcirc	\bigcirc	\bigcirc	0
I have accomplished many worthwhile things in this job.	0	\bigcirc	\bigcirc	\bigcirc	\bigcirc	\bigcirc	\bigcirc
I just want to do my job and not be bothered.	0	\bigcirc	\bigcirc	\bigcirc	\bigcirc	\bigcirc	\bigcirc
I have become more cynical about whether my work contributes anything.	0	\bigcirc	\bigcirc	\bigcirc	\bigcirc	0	0
I doubt the significance of my work.	0	\bigcirc	\bigcirc	\bigcirc	\bigcirc	\bigcirc	\bigcirc
At my work, I feel confident that I am effective at getting things done.	0	\bigcirc	\bigcirc	\bigcirc	\bigcirc	0	0

Copyright ©1996 Wilmar B. Schaufeli, Michael P. Leiter, Christina Maslach & Susan E. Jackson. All rights reserved in all media. Published by Mind Garden, Inc., www.mindgarden.com

STSS (Secondary Traumatic Stress Scale)

The following is a list of statements made by persons who have been impacted by their work with traumatized clients (or other potentially traumatized populations, e.g., patients, students, customers, or anyone to whom you provide services).

In the **past seven** days, how frequently was the statement true for you:

	Never	Rarely	Occasionally	Often	Very often
I felt emotionally numb.	0	\bigcirc	0	0	0
My heart started pounding when I thought about my work with clients.	0	\bigcirc	0	\bigcirc	\bigcirc
It seemed as if I was reliving the trauma(s) experienced by my client(s).	0	\bigcirc	0	\bigcirc	\bigcirc
I had trouble sleeping.	0	\bigcirc	0	\bigcirc	\bigcirc
I felt discouraged about the future.	0	\bigcirc	0	\bigcirc	\bigcirc
Reminders of my work with clients upset me.	0	\bigcirc	0	\bigcirc	\bigcirc
I had little interest in being around others.	0	\bigcirc	0	\bigcirc	0
I felt jumpy.	0	\bigcirc	0	\bigcirc	\bigcirc
I was less active than usual.	0	\bigcirc	0	\bigcirc	\bigcirc
I thought about my work with clients when I didn't intend to.	0	\bigcirc	0	\bigcirc	0
I had trouble concentrating.	0	\bigcirc	0	\bigcirc	\bigcirc
I avoided people, places, or things that reminded me of my work with clients.	0	\bigcirc	0	\bigcirc	0
I had disturbing dreams about my work with clients.	0	\bigcirc	0	\bigcirc	\bigcirc
I wanted to avoid working with some clients.	0	\bigcirc	0	\bigcirc	0
I was easily annoyed.	\bigcirc	\bigcirc	0	\bigcirc	\bigcirc
I expected something bad to happen.	0	\bigcirc	\bigcirc	\bigcirc	0
I noticed gaps in my memory about client sessions.	\bigcirc	\bigcirc	0	\bigcirc	0

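### Page 2 of the student burnout scale (MBI-S) carries the job-version instruction over student statements and contradicts page 1: a minor correction, best made before fielding

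*Combined protocol and SAP*

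**What the plan says.** In the student survey the MBI-S is one scale split over two pages. The page 1 instruction begins "Below are 17 statements of university-related feelings" and continues "Please read each statement and decide if you ever feel this way about your academic work". Eight statements follow. After the copyright notice, page 2 begins "On this page are statements of job-related feelings. Please read each statement carefully and decide if you ever feel this way about your job" and prints eight more.

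The same job instruction appears in the MBI-GS, which comes next in the student survey, and in the burnout section of the victim service provider survey. In both of those places it introduces job statements and is correct.

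Table 1 of the protocol lists "Student Version* MBI-S 16", and the note to its starred rows says "All items may not actually appear in each survey". The protocol's account of the two student cohorts says that the survey will be used to evaluate the content and effectiveness of the course. The SAP names STSS and PCL-5 as outcome measures, plans mostly descriptive statistics at each wave, and does not mention the MBI-S.

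**The concern.** The survey keeps two kinds of burnout apart: the MBI-S for study and the MBI-GS for paid or voluntary work. An instruction that changes the setting halfway through the study scale works against that separation.

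The weak spot is the page 2 statement "I just want to get my work done and not be bothered", which names no setting of its own. If it is answered about a job, it asks nearly the same thing as the MBI-GS statement "I just want to do my job and not be bothered", and the two scales overlap where they were meant to differ. As the survey is laid out, students without a job also meet the job heading, because the direct question on work status opens the MBI-GS and so comes after the MBI-S.

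What is exposed is how a reported MBI-S level should be read, and any comparison between cohorts that were shown different headings.

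**Working it through.** **1. Does the job heading belong to the MBI-S?** The order in the student survey is: MBI-S label, university instruction, eight rows, copyright notice, job instruction, eight rows, copyright notice, MBI-GS label, work-status question, and then the MBI-GS's own job instruction. The eight rows under the first job instruction are student statements. That instruction is therefore page 2 of the MBI-S. Both instructions are running text, so a broken table does not explain the contradiction.

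**2. The count of statements.** Page 1 announces 17.

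- Rows printed: 8 (page 1) + 8 (page 2) = 16.
- Table 1 entry for MBI-S: 16, which the printed rows reproduce.
- Difference from the announced number: 17 − 16 = 1.

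The note to Table 1 allows fewer items than listed, so it cannot turn 16 into 17. Table 1 gives 17 for the MBI-GS, which prints 16 statements and one work-status question (16 + 1 = 17). The documents do not say whether the 17 was carried over from there.

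**3. Which statements rely on the heading?** Each of the 16 rows was sorted by the academic word it contains.

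| Page | Instruction refers to | *studies* | *university* | *class(es)* | *student* | none | Rows |
|---|---|---|---|---|---|---|---|
| 1 | academic work | 4 | 2 | 2 | 0 | 0 | 8 |
| 2 | job | 3 | 3 | 0 | 1 | 1 | 8 |

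Statements with an academic word: 8 + 7 = 15 of 16. Statements without one: 1 of 16 = 6.25%.

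**4. Range.** The student demographics ask about hours of paid work on campus. A student with such a job, reading under the job heading, might take the three page 2 statements that say *university*, such as "I have become more cynical about whether my university work contributes to anything", to mean that job. This reading is possible but not shown. It would give 1 + 3 = 4 of 16 = 25%. The other 12 (8 on page 1, plus 3 with *studies* and 1 with *student* on page 2) are academic on any reading.

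**5. Effect on scores.** This cannot be computed, because the documents define no MBI-S score or subscale. About 15 + 35 = 50 students are planned. That is the number who could see the heading, not the number who would misread it, and participation is optional.

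**The case against.** The strongest reply is that this is copy-editing. Fifteen of the 16 statements name their own setting. The sixteenth sits inside a student scale: it follows a statement about studies and comes just before "I have become more cynical about whether my university work contributes to anything", and page 1 has already set the academic frame. That anyone would answer it about a job is conjecture. The SAP defines no MBI-S analysis, and nothing is calculated from the announced 17. One student survey is attached for both cohorts, so a difference in headings would arise only if the text were changed part-way.

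Most of this stands, and it sets the size of the point. It does not remove the contradiction. The heading is text put to participants, in a survey that the protocol uses to judge the course, and for one statement the heading is wrong where the wording gives no setting. The risk of creating unlike cohorts is a reason to correct the heading before fielding and to leave it alone within a cohort.

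A reader might infer that half the scale (8 of 16) measures job burnout. The documents do not support that: eight statements sit under the wrong heading, but seven of them carry academic words. Nor do they show that a seventeenth statement was lost, since the 16 rows agree with Table 1.

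**Conclusion.** The point holds as a minor correction. The two pages of the MBI-S give contradictory instructions, and at least 1 of 16 statements (6.25%) takes its setting from the wrong one. The figure is 4 of 16 (25%) on the least favourable reading, and then only for students employed on campus. The size of any error in scores is unknown and should be small, because most statements identify their own setting.

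Change between waves is less exposed than level. A misreading largely cancels if the heading stays the same and each student reads it the same way each time; it need not cancel if a student's job situation changes between waves.

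A reader might infer that a planned analysis of the trial is compromised. It is not: the SAP's named outcomes are STSS and PCL-5, and neither uses these statements. The mismatch of 17 with 16 is clerical.

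The conclusion assumes that the attached survey is the text fielded. The terms of the licensed form are not in the documents, nor is there any sign of which instruction came from it.

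**What to change.** - Before fielding, replace the MBI-S page 2 heading with the university wording of page 1, through a minor IRB amendment. First check that the terms of the copyrighted form allow the edit.
- If a cohort has already begun with the job heading, keep it for that cohort's remaining waves, and report which cohort saw which heading.
- In the same edit, reconcile the announced 17 with the 16 statements printed and listed in Table 1, checking the number against the licensed form.

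The cost is one heading, one number and one amendment form. The investigators have already used that route to request adding the self-compassion scale to the survey. The SAP needs no change.

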Please select 'Very often' for this response.	0	0	0	0	0

PCL-5 (PTSD)

Below is a list of problems that people sometimes have in response to a very stressful experience. Please read each problem carefully and then indicate how much you have been bothered by that problem in the past month.

In the **past month**, how much were you bothered by:

	Not at all	A little bit	Moderately	Quite a bit	Extremely
Repeated, disturbing, and unwanted memories of the stressful experience?	0	0	0	0	0
Repeated, disturbing dreams of the stressful experience?	0	\bigcirc	0	0	\bigcirc
Suddenly feeling or acting as if the stressful experience were actually happening again (as if you were actually back there reliving it)?	0	\bigcirc	\bigcirc	0	\bigcirc
Feeling very upset when something reminded you of the stressful experience?	0	0	0	\circ	0

Having strong physical reactions when something reminded you of the stressful experience (for example, heart pounding, trouble breathing, sweating)?	0	\bigcirc	0	0	\bigcirc	
Avoiding memories, thoughts, or feelings related to the stressful experience?	0	0	\bigcirc	\bigcirc	0	
Avoiding external reminders of the stressful experience (for example, people, places, conversations, activities, objects, or situations)?	0	\bigcirc	\bigcirc	\bigcirc	\bigcirc	
Trouble remembering important parts of the stressful experience?	0	\bigcirc	0	0	0	
Having strong negative beliefs about yourself, other people, or the world (for example, having thoughts such as: I am bad, there is something seriously wrong with me, no one can be trusted, the world is completely dangerous)?	0	0	0	0	0	
Blaming yourself or someone else for the stressful experience or what happened after it?	0	\bigcirc	\bigcirc	\bigcirc	\bigcirc	

Below is a list of problems that people sometimes have in response to a very stressful experience. Please read each problem carefully and then indicate how much you have been bothered by that problem in the past month.

In the **past month**, how much were you bothered by:

	Not at all	A little bit	Moderately	Quite a bit	Extremely
Having strong negative feelings such as fear, horror, anger, guilt, or shame?	0	\bigcirc	\bigcirc	0	0
Loss of interest in activities that you used to enjoy?	0	\bigcirc	0	0	\bigcirc
Feeling distant or cut off from other people?	0	\bigcirc	0	0	\bigcirc
Trouble experiencing positive feelings (for example, being unable to feel happiness or have loving feelings for people close to you)?	0	\bigcirc	0	\bigcirc	\bigcirc

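### Does the attention-check line in the STSS grid inflate a named outcome, given that Table 1 lists the scale at 18 items?

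*Combined protocol and SAP*

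**What the plan says.** Protocol section VII.B, Table 1, gives the line count of each questionnaire. Two rows matter here: "Secondary Traumatic Stress Scale STSS 18" and "Five Facets of Mindfulness Questionnaire FFMQ 20". Neither carries an asterisk, so the footnote "Note: *All items may not actually appear in each survey" does not cover them.

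In the student survey the STSS block runs from "I felt emotionally numb" to "I noticed gaps in my memory about client sessions" and ends with the line "Please select 'Very often' for this response". All lines share the response options "Never Rarely Occasionally Often Very often". The survey for victim service providers has the same block. An identical check sits on the first page of the FFMQ in both surveys.

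The SAP, which covers the student pilot sample, says: "For each outcome measure (i.e., STSS, PCL-5), most analyses will simply involve calculating descriptive statistics for each wave of data collection". It gives no scoring rule for the STSS and no rule for respondents who fail a check.

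**The concern.** The check shares the grid and the scale of a named outcome, and the only item count the documents give for that outcome includes it. An analyst who took 18 as the scale length and summed every line would add the maximum item score for each attentive respondent. The total would then have the wrong range and could not be set beside a 17-item score. A respondent who passed the check at the first wave and failed it at the second would show a lower trauma score for no clinical reason, so inattention could pass for benefit. The pilot is meant to inform later designs, so a distorted level could be carried forward. The checks are also collected without any stated use, and the FFMQ count in the same table is plainly off, which makes the table look unreliable.

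**Working it through.** **Count.** Inputs: the STSS block in both surveys and Table 1. There are 17 symptom lines and 1 check, and 17 + 1 = 18, which is the Table 1 figure. Without the check the count is 17. For the FFMQ the three pages hold 13 + 13 + 13 = 39 statements, or 40 lines with the check. Table 1 says 20, which matches neither.

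**What the item column counts.** Table 1 lists questionnaires under the question on research procedures and contains no scoring.
- Its unstarred Feedback row has 2 items, both free-text questions with no score.
- The demographic blocks are listed with item counts in the same way.
- The general student burnout version is listed at 17. The form shows 8 + 8 = 16 burnout statements plus one yes/no question on whether the student works, and 16 + 1 = 17. That row is starred, so this match is suggestive rather than conclusive.

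The column is best read as lines presented to the respondent. On that reading 18 is correct for the STSS.

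**Level effect if all 18 lines were summed.** The survey prints no numeric codes, so both usual codings are shown.
- 1-5 coding: the range is 17-85 over 17 lines and 18-90 over 18. A passing respondent gains 5.
- 0-4 coding: the range is 0-68 over 17 lines and 0-72 over 18. A passing respondent gains 4.

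The relative inflation under 1-5 coding is 5 / (17 × item mean). The item means are assumed:

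| Item mean | 17-line total | 18-line total | Increase |
|---|---|---|---|
| 1.5 | 25.5 | 30.5 | 19.6% |
| 2.0 | 34 | 39 | 14.7% |
| 3.0 | 51 | 56 | 9.8% |

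**Change between waves.** A respondent who passes at both waves carries the same constant twice, so it drops out. For the group, the spurious change in the mean total is −d × (f2 − f1). Here f1 and f2 are the check-failure rates at the earlier and later wave, and d is the average number of points lost on the check line by those who fail (1 to 4 under either coding). With assumed rates:
- 0% then 10%: −0.1 (d = 1) to −0.4 (d = 4), an apparent improvement.
- 10% then 10%: 0.
- 10% then 0%: +0.1 to +0.4, an apparent worsening.

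The two student cohorts are planned at about 15 and 35, so 50 together. One additional failure at the later wave moves the mean by at most 4 / 50 = 0.08 points.

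**Other named outcome.** The PCL-5 form has 10 + 10 = 20 lines and no check, which agrees with its Table 1 entry of 20.

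**The case for a change.** The best argument for a change is that the rule is missing for a named outcome and that supplying it costs one sentence. The check lies inside the outcome's own grid, on its own scale, so an export that sums the block would pick it up. The burnout work question is a weaker parallel, because it stands outside its grid and has a different answer format. The level effect, at 10% to 20% of a plausible total, would matter to anyone who used pilot means to plan a later study.

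Part of this stands. The counts are right, the SAP has no scoring rule, and an 18-line sum would be wrong. But the step from a line count in a table to a scored item is an inference that no text supports. The line tells the respondent which option to tick; it says nothing about a symptom. Investigators who put such a line into two questionnaires did so to detect careless answering, and are not likely to score it as a symptom of trauma. The FFMQ entry points the same way: a table that is out by 19 or 20 lines on one scale cannot serve as the scoring key for another.

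The claim that careless answering would look like improvement does not hold in general. It needs the check to be summed and failures to be more frequent later; the opposite pattern gives the opposite sign. The SAP plans no cut-off and no external comparison, so harm to either depends on a use it does not state. On failed checks the plan is silent. It does not commit to keeping those responses, and either choice is workable in a descriptive pilot if it is reported.

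**Conclusion.** The concern does not call for a change. The observation about the counts is correct: Table 1 reaches 18 for the STSS by including the attention check, and its FFMQ figure is a clerical error on a measure outside the outcomes the SAP names. The inflation of 4 or 5 points is hypothetical, because it arises only if the check is scored, and the documents do not direct that. Even then, comparisons between waves would be disturbed only by a shift in failure rates, by 0.1 to 0.4 points on the mean total for a ten-point shift, in either direction.

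This rests on two assumptions: that the item column counts lines shown rather than items scored, and that analysts who wrote the check know it is not a symptom. Both are reasonable on the face of the forms. Followed as written, the plan for per-wave descriptives gives no wrong result. The unwritten convention can be settled in the scoring syntax and described when results are reported.
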